3.4 SECONDARY ENDPOINTS

Table 7: Secondary Objectives and Associated Endpoints

Phase 2 Secondary Objectives Phase 2 Secondary Endpoints	
1. Evaluate the safety and tolerability of INO-4800 administered by ID	1a. Incidence of solicited and unsolicited injection site reactions
injection followed immediately by EP	1b. Incidence of solicited and unsolicited systemic adverse events (AEs) by system organ class (SOC), preferred term (PT), severity and relationship to investigational product
	1c. Incidence of serious adverse events (SAEs)
	1d. Incidence of adverse events of special interest (AESIs)
Phase 3 Secondary Objectives	Phase 3 Secondary Endpoints
1. Evaluate the safety and tolerability of INO-4800	 Incidence of solicited and unsolicited injection site reactions
	1b. Incidence of solicited and unsolicited systemic adverse events (AEs) by system organ class (SOC), preferred term (PT), severity and relationship to investigational product
	1c. Incidence of serious adverse events (SAEs)
	1d. Incidence of adverse events of special interest (AESIs)
	1e. Incidence of all-cause mortality
2. Evaluate efficacy of INO-4800 in the prevention of COVID-19 disease according to degrees of disease severity in subjects who are SARS-	2a. Incidence of non-severe COVID-19 disease in SARS-CoV-2 seronegative subjects starting 14 days after completion of the 2-dose regimen until EOS
CoV-2 seronegative at baseline	2b. Incidence of severe COVID-19 disease in SARS- CoV-2 seronegative subjects starting 14 days after completion of the 2-dose regimen until EOS

		2c. Incidence of deaths due to COVID-19 in SARS- CoV-2 seronegative subjects starting 14 days after completion of the 2-dose regimen until EOS
3.	Evaluate the cellular and humoral immune response to INO-4800	3a. Antigen-specific cellular immune response measured by IFN-gamma ELISpot
		3b. Neutralizing antibody response measured by a pseudovirus-based neutralization assay
4.	Evaluate the efficacy of INO-4800 in the prevention of COVID-19 disease in subjects who are SARS- CoV-2 seropositive at baseline	 Incidence of virologically-confirmed COVID-19 disease starting 14 days after completion of the 2-dose regimen until 12 months post-dose 2 (End of Study (EOS)) in subjects who are SARS- CoV-2 seropositive at baseline

3.5 **EXPLORATORY OBJECTIVE**

See Table 8.

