The diary should be completed once daily starting the evening of each study dose through 6 days post-dose. The completed diary post-dose 1 and post-dose 2 will be reviewed with the subject by the study staff during the next study phone call or visit and collected at the next in-person study visit. The study staff will review the diary with the subject to assess for temperature, solicited systemic symptoms (unusually tired/feeling unwell, muscle aches, headache, nausea, joint pain) and solicited injection site symptoms (pain, itching, redness, swelling, bruising). In addition, unsolicited symptoms and concomitant medications will be assessed.

Any diary entry determined to meet the Common Terminology Criteria for Adverse Events version 5.0 (CTCAE) criteria for a Grade 1 or higher adverse event should be documented as an adverse event unless deemed part of the subject's ongoing medical history. Injection site reactions should be graded per the Toxicity Grading Scale for Healthy Adult and Adolescent Volunteers Enrolled in Preventive Vaccine Clinical Trials, issued September 2007 (See Section 6.4.5). If the diary entry does not meet the criteria of a Grade 1 or higher AE as per the relevant guidelines, Investigator clinical judgment can be used to determine whether the entry should be recorded as an AE and documented accordingly in the site's source. For cases where the diary entry and final AE reporting (i.e. grading) do not agree, the reasoning should be recorded in the source documents.

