6.4.5 ASSESSMENT OF INJECTION SITE REACTIONS

Reactions arising from the IP administration procedure may be reported as administration site or injection site reactions. When evaluating administration (injection) site reactions throughout the study, it is most important to be as specific as possible by selecting the most appropriate term (see Table 10 below) and using the grading scale as listed in the Toxicity Grading Scale for Healthy Adult and Adolescent Volunteers Enrolled in Preventive Vaccine Clinical Trials, issued September 2007. All subjects will be observed for 30 minutes following the IP administration procedure for immediate AEs. In addition, other events associated with administration (injection) site reactions (e.g., hematoma, infection or necrosis) should also be reported with preferred terms specific for administration (injection) site reactions.

Local Reaction to Injectable Product (Grade)	Mild (1)	Moderate (2)	Severe (3)	Potentially Life Threatening (4)
Pain	Does not interfere with activity	Repeated use of non- narcotic pain reliever >24 hours or interferes with activity	Any use of narcotic pain reliever or prevents daily activity	Emergency room visit or hospitalization
Tenderness	Mild discomfort to touch	Discomfort with movement	Significant discomfort at rest	ER visit or hospitalization
Erythema/Redness ^a	2.5-5 cm	5.1-10 cm	>10 cm	Necrosis or exfoliative dermatitis
Induration/Swelling ^b	2.5-5 cm and no	5.1-10 cm or interferes with activity	>10 cm or prevents daily activity	Necrosis

Protocol Version: 2.0USA

interference			
w/ activity			
September 2007 "EDA Guidance for Industry-Toxicity Grading Scale for Healthy Adult and Adolescent			

September 2007 "FDA Guidance for Industry-Toxicity Grading Scale for Healthy Adult and Adolescent Volunteers Enrolled in Preventive Vaccine Clinical Trials"

^a In addition to grading the measured local reaction at the greatest single diameter, the measurement should be recorded as a continuous variable

^b Should be evaluated and graded using the functional scale as well as the actual measurement.

6.4.6 **CONCOMITANT MEDICATIONS/TREATMENTS**

All medications (prescription and nonprescription, including receipt of any non-study COVID-19 vaccine (authorized under emergency use or licensed)) taken between informed consent and study discharge (see Section 4.2) must be recorded on the CRFs.

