7.0 EVALUATION OF SAFETY AND MANAGEMENT OF TOXICITY

7.1 SAFETY PARAMETERS

The safety of INO-4800 will be measured and graded in accordance with the Common Terminology Criteria for Adverse Events (CTCAE), version 5.0.

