8.5.3 SAFETY ANALYSES

8.5.3.1 Adverse Events

All AEs including injection-site reactions will be summarized among the Safety Population by frequency per treatment arm. These frequencies will be presented overall and separately by dose, and will depict overall, by system organ class and by preferred term, the percentage of subjects affected. Additional frequencies will be presented with respect to maximum severity and to strongest relationship to Study Treatment. Multiple occurrences of the same AE will be counted only once following a worst-case approach with respect to severity and relationship to Study Treatment. All serious AEs will also be summarized as above.

The main summary of safety data will be based on events occurring within 30 days of any dose. For this summary, the frequency of preferred term events will be compared between study arms with risk differences and 95% confidence intervals, using the method of Miettinen and Nurminen. As this analysis will use many event categories, and produce many confidence intervals, caution should be exercised when interpreting these confidence intervals. Separate summaries will be based on events occurring within 7 days of any dose and regardless of when they occurred.

The analyses listed above will be performed according to the Phase of the trial. For the Phase 2 segment, the analyses listed above will also be performed according to prior receipt of any non-study prophylactic COVID-19 vaccine. For the Phase 3 segment, the analyses listed above will also be performed according to SARS-CoV-2 serostatus at baseline.

For AE data, partial start dates will be imputed to the date of treatment to conservatively report the event as treatment-emergent, whenever the portion of the date is consistent

INO-4800	COVID19-311
Inovio Pharmaceuticals, Inc.	Clinical Protocol

with that of the study treatment. Otherwise, it will be imputed to the earliest date consistent with the partial date. A completely missing onset date will be imputed as the day of treatment. Partial stop dates will be assumed to be the latest possible day consistent with the partial date. AE duration will be calculated as (Stop Date – Start Date) + 1.

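### Endpoint 1a counts solicited local reactions only once recorded as adverse events, but two scales are named without saying which governs, and the local one has no row for itching or bruising

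*Protocol*

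**What the plan says.** - **Endpoint.** Protocol Section 3.4, Table 7, endpoint 1a for Phase 2 and for Phase 3: "Incidence of solicited and unsolicited injection site reactions".
- **What is solicited.** Section 6.4, Diary, lists "solicited injection site symptoms (pain, itching, redness, swelling, bruising"), completed daily from the evening of each dose through six days after it.
- **Route to AE status.** The same section says that any diary entry meeting the CTCAE v5.0 "criteria for a Grade 1 or higher adverse event should be documented as an adverse event", unless it belongs to the subject's ongoing medical history. The next sentence says "Injection site reactions should be graded per the Toxicity Grading Scale for Healthy Adult and Adolescent Volunteers" (the September 2007 scale). Then: "If the diary entry does not meet the criteria of a Grade 1 or higher AE as per the relevant guidelines, Investigator clinical judgment" may settle whether the entry is recorded.
- **Local scale.** Section 6.4.5 repeats the instruction, "using the grading scale as listed in the Toxicity Grading Scale for Healthy Adult and Adolescent Volunteers", and prints a table with rows for pain, tenderness, erythema/redness and induration/swelling.
- **General scale.** Section 7.1: "The safety of INO-4800 will be measured and graded in accordance with the Common Terminology Criteria for Adverse Events". Section 7.10.3 also has the investigator grade clinical AEs by CTCAE.
- **Analysis.** Section 8.5.3.1: "All AEs including injection-site reactions will be summarized among the Safety Population by frequency per treatment arm", with further frequencies by maximum severity. No tabulation of diary entries is described. Section 8.1 states that the formal analysis plan is the text of Section 8 itself.

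**The concern.** A solicited reaction is collected by asking every subject about the same symptoms on the same days, so that its incidence does not depend on who chooses to report what. Here a further step stands between the diary and the endpoint: the site must record the entry as an AE. For some of the solicited symptoms the rule for that step is either ambiguous or discretionary.

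Two sites could follow the text in good faith and treat an identical entry differently. At stake are the incidence and maximum severity of local reactions, which the protocol itself expects to be frequent: Table 5 in Section 1.4.2.1 puts injection site pruritus in the very common band (10% or more) and bruising in the common band (1% to under 10%). The primary efficacy endpoint is not affected.

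**Working it through.** The protocol gives no figure to reproduce, so the check sets the diary list against the grading table and then follows an entry through the recording and analysis rules.

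**Step 1. Coverage of the five solicited local symptoms by the table in Section 6.4.5.**

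| Diary symptom | Row in table | Lowest entry point |
|---|---|---|
| Pain | yes | Grade 1, no interference with activity |
| Redness | yes | Grade 1 at 2.5 cm; nothing by size below that |
| Swelling | yes | Grade 1 at 2.5 cm; at any size Grade 2 if it interferes with activity |
| Itching | no | none |
| Bruising | no | none |

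Two of five symptoms have no grade and two more have a size floor, which for swelling the functional criterion overrides. Tenderness has a row but is not among the solicited symptoms.

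**Step 2. One entry, two readings.** Take a subject who records itching on all seven diary days.
- If CTCAE decides, the entry should be an AE provided CTCAE gives it at least Grade 1. The content of CTCAE is not in the protocol, so that cannot be settled from it.
- If the 2007 scale decides because this is an injection site reaction, there is no Grade 1 criterion to meet, and recording is at the investigator's discretion.

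The phrase about relevant guidelines in Section 6.4 does not choose between the two. Naming CTCAE in Sections 7.1 and 7.10.3 does not remove the specific instruction in Sections 6.4 and 6.4.5 to use the other scale for local reactions.

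**Step 3. From record to endpoint.** Section 8.5.3.1 summarises AEs. An entry not recorded as an AE appears nowhere in the described analysis of endpoint 1a. An itching or bruising entry that is recorded has no severity on the scale required for it.

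**Step 4. How many subjects the ambiguity could touch (scale only).** Section 6.4 estimates 711 Phase 3 diary subjects. Assuming they split 2:1 like the trial, 711 × 2/3 = 474 receive INO-4800. Applying the Table 5 bands:
- itching, at the 10% floor: 474 × 0.10 ≈ 47 subjects or more;
- bruising, 1% to 10%: 474 × 0.01 ≈ 5 to 474 × 0.10 ≈ 47 subjects.

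These are subjects whose entries fall under the unclear rule, not subjects shown to be lost.

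**Step 5. Effect on the arm comparison.** If a fraction f of true reactions is recorded in each arm, the observed risk difference is f × p1 − f × p0 = f × (p1 − p0). Under-recording that is equal in both arms therefore still shrinks the difference by the factor f. The protocol gives no value of f.

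**The case against.** The best case for the text is that capture is wider than the 2007 table suggests.
- An entry below Grade 1 may still be recorded, and any entry reaching CTCAE Grade 1 should be.
- Subjects are asked about injection site reactions at visits and calls (Section 6.4.4).
- Section 6.4.5 wants other local events, such as hematoma, reported under specific terms.
- Redness diameter is also kept as a continuous measurement.
- Section 7.10.3 offers a CTCAE severity route, and Section 1.3.5 reports a Grade 2 injection site pruritus in the Phase 1 trial, so the sponsor has graded itching before.
- Disagreement between diary and AE grading must be explained in the source documents.
- Phase 3 is double-blind, so discretion is not tied to the arm.

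All of this stands, and it limits the point. None of it says which scale governs a local diary entry, or provides a diary-based analysis. Blinding protects against differential recording in Phase 3, but not against the shrinkage in Step 5. In Phase 2, Section 8.7 describes blinding only within dose group, so recording there is not masked to the number of injections.

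Two stronger readings are tempting. A reader might infer that only graded events count; the text does not say so, since ungraded entries can be recorded. A reader might also infer that reactogenicity is understated, for example that a true 10% itching rate would be reported as 5% if half the entries were recorded. The protocol gives no recording fraction, and the Table 5 bands are cited to the Investigator's Brochure as frequencies already reported, so they do not demonstrate a loss.

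The wording is the same in the two full versions shown (1.0USA and 2.0USA). The body of Version 7.0, whose closing pages also appear, is not shown and could not be checked.

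**Conclusion.** The mismatch is real. The solicited list, the grading table, the recording rule and the analysis rule do not fit together for itching, bruising and small areas of redness or swelling. The incidence and severity of solicited local reactions may be under-captured and may vary between sites. The direction is plausible and the size is unknown; neither a bias nor a difference between arms has been shown.

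The conclusion rests on reading Section 8 as the formal analysis plan, as Section 8.1 states, and on no other document in the trial fixing the governing scale. It concerns a named secondary safety endpoint in both segments. The change is a cheap improvement rather than a repair of the trial's main result.

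**What to change.** 1. In Section 8.5.3.1, tabulate solicited local reactions for endpoint 1a directly from the diary: a subject has the reaction if it is recorded on any diary day. Show redness and swelling under 2.5 cm as a separate ungraded category.
2. Reconcile Sections 6.4, 6.4.5, 7.1 and 7.10.3 by naming the one scale that grades itching and bruising.
3. Keep investigator-recorded AEs as a separate table, so that clinical judgment remains visible without determining the solicited incidence.

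The cost is a few lines of text and one extra table from diaries already collected. Reported reaction rates would probably be somewhat higher. The small-size category depends on the diameter being available; Section 6.4.5 already asks for redness as a continuous measurement and for swelling to be measured.

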6.4.1 INTRADERMAL INJECTION AND EP

Phase 2 and Phase 3 segments:

A complete administration procedure is defined as an ID injection (formation of a wheal) of IP followed by insertion of the ID Array needles (electrodes) through the skin and into the wheal followed by delivery of four electroporation pulses. This procedure is broadly described as administration because it involves more than the injection of a drug.

Only if the deltoid area is not a suitable location for administration (see exclusion criterion 'j'), the ID injection can then be administered above the lateral quadriceps followed immediately by EP. IP must not be given within 2 cm of a tattoo, scar, keloid, or active lesion/rash. Also, ID injection followed immediately by EP must not be performed on the skin of an extremity which has any metal implants or implantable medical device (e.g., surgical rods, pins or joint replacements). If a subject has an implanted cardiac defibrillator or pacemaker, ID injection/EP must not be performed above the deltoid muscle on the same side of the body where the device is located.

There are three steps that must be performed as part of the administration procedure:

- 1. Injection of IP (INO-4800 or placebo)
- 2. Insertion of the array into the subject's skin

INO-4800	COVID19-311
Inovio Pharmaceuticals, Inc.	Clinical Protocol

3. Pressing the trigger button on the EP applicator

Table 9 below is provided as guidance on how to appropriately complete the procedure when injection of IP has occurred, but the subject did not receive EP.

Table 9: Guidance for how to manage an incomplete administration after IP has	
been injected	

Was IP injected?	Was the array inserted into skin?	Was trigger button pressed?	Action
Yes	Yes (if array gets dislodged before the trigger button is pressed, the same array may be re-inserted)	No	If the drug injection wheal is discernable, EP should be attempted at the site of drug injection to complete the procedure
Yes	No	Yes	If the drug injection wheal is discernable, EP should be attempted at the site of drug injection to complete the procedure
Yes	No	No	If the drug injection wheal is discernable, EP should be attempted at the site of drug injection to complete the procedure

Reinjection of IP (i.e. protocol-specified IP has already been delivered) is not permitted. Delivery of a second electroporation in tissue is not permitted.

Training will be provided by the Sponsor on use of the device.

Phase 2 segment:

Subjects will receive a two-dose regimen of one or two 1.0 mg ID injections of INO-4800 or placebo in a volume of ~0.1 mL in an acceptable skin location for injection and subsequently followed immediately by EP of each injection site with CELLECTRA[®] 2000 at Day 0 and Day 28. For subjects assigned to receive two injections + EP at each dosing visit, the two injections must be performed in acceptable locations on two different limbs.

Phase 3 segment:

Subjects will receive a two-dose regimen of two 1.0 mg ID injections of INO-4800 or placebo in a volume of ~0.1 mL in an acceptable skin location for injection on different limbs and subsequently followed immediately by EP of the injection site with CELLECTRA[®] 2000 at Day 0 and Day 28.

6.4.2 MANAGEMENT OF PAIN DUE TO ELECTROPORATION (EP) PROCEDURES

In case of pain, subjects may be treated with a non-narcotic analgesic (e.g., acetaminophen) after injection/EP.

Medication taken for pain management will be documented as concomitant medications.

6.4.3 ASSESSMENT OF LABORATORY ABNORMALITIES

INO-4800	COVID19-311
Inovio Pharmaceuticals, Inc.	Clinical Protocol

In Phase 2, samples will be collected for serum chemistry, hematology, and urinalysis at the visits listed in the Schedule of Events (Tables 3 and 4) and as listed in Section 6.4.

Laboratory AEs will be assessed and graded in accordance with the Common Terminology Criteria for Adverse Events (CTCAE), version 5.0. Laboratory values that are not clinically significant (NCS) in the Investigator's opinion will not be reported as AEs.

6.4.4 ASSESSMENT OF CLINICAL TRIAL ADVERSE EVENTS (AES)

Subjects will be queried regarding the occurrence of any AEs including AEs related to injection site reactions, concomitant medications and new onset illness or disease during their study visits and phone calls. Subjects will be reminded to contact study personnel and immediately report any event for the duration of the study. All AEs will be captured from the time of the informed consent until 28 days post-dose 2 (Day 56). Following the Day 56 visit, only SAEs, AESIs and MAAEs will be collected. All related AEs, AESIs and SAEs will be followed to resolution or stabilization. These events will be recorded on the subject's CRF.

6.4.5 ASSESSMENT OF INJECTION SITE REACTIONS

Reactions arising from the IP administration procedure may be reported as administration site or injection site reactions. When evaluating administration (injection) site reactions throughout the study, it is most important to be as specific as possible by selecting the most appropriate term (see Table 10 below) and using the grading scale as listed in the Toxicity Grading Scale for Healthy Adult and Adolescent Volunteers Enrolled in Preventive Vaccine Clinical Trials, issued September 2007. All subjects will be observed for 30 minutes following the IP administration procedure for immediate AEs. In addition, other events associated with administration (injection) site reactions (e.g., hematoma, infection or necrosis) should also be reported with preferred terms specific for administration (injection) site reactions.

Local Reaction to Injectable Product (Grade)	Mild (1)	Moderate (2)	Severe (3)	Potentially Life Threatening (4)
Pain	Does not interfere with activity	Repeated use of non- narcotic pain reliever >24 hours or interferes with activity	Any use of narcotic pain reliever or prevents daily activity	Emergency room visit or hospitalization
Tenderness	Mild discomfort to touch	Discomfort with movement	Significant discomfort at rest	ER visit or hospitalization
Erythema/Redness ^a	2.5-5 cm	5.1-10 cm	>10 cm	Necrosis or exfoliative dermatitis
Induration/Swelling ^b	2.5-5 cm and no	5.1-10 cm or interferes with activity	>10 cm or prevents daily activity	Necrosis

Protocol Version: 2.0USA

interference			
w/ activity			
September 2007 "EDA Guidance for Industry-Toxicity Grading Scale for Healthy Adult and Adolescent			

September 2007 "FDA Guidance for Industry-Toxicity Grading Scale for Healthy Adult and Adolescent Volunteers Enrolled in Preventive Vaccine Clinical Trials"

^a In addition to grading the measured local reaction at the greatest single diameter, the measurement should be recorded as a continuous variable

^b Should be evaluated and graded using the functional scale as well as the actual measurement.

6.4.6 **CONCOMITANT MEDICATIONS/TREATMENTS**

All medications (prescription and nonprescription, including receipt of any non-study COVID-19 vaccine (authorized under emergency use or licensed)) taken between informed consent and study discharge (see Section 4.2) must be recorded on the CRFs.

Actual or estimated start and stop dates must be provided. This information will be obtained from the subject and/or any available medical records. The indication for the medication, dose, and dose regimen will be documented.

Therapy considered necessary for the subject's welfare may be given at the discretion of the Investigator or medical provider. If the permissibility of a specific medication/treatment is in question, please contact the Medical Monitor.

The decision to administer a prohibited medication/treatment (Section 6.4.7) is made with the safety of the clinical trial subject as the primary consideration. When possible, the Sponsor should be notified before the prohibited medication/treatment is administered.

6.4.7 **RESTRICTIONS**

In the Phase 2 segment of the trial, subjects should refrain from becoming pregnant until 3 months following the last dose of investigational product by using appropriate contraceptive measures (see Section 4.1.1). In the Phase 3 segment of the trial, subjects should refrain from becoming pregnant until receipt of the last dose of investigation product by using appropriate contraceptive measures (See Section 4.1).

Subjects must not receive any non-study related vaccine (e.g., influenza vaccine) within 2 weeks prior to the first dose of IP, or within 2 weeks of (before or after) any subsequent dose of IP.

Subjects must not have fever (oral temperature \geq 38.0 degrees Celsius or 100.4° Fahrenheit) within 72 hours prior to each dosing.

Subjects should not receive hydroxychloroquine during the trial. In the Phase 3 segment, subjects should not receive any other drug/vaccine intended as COVID-19 prophylaxis during the trial. Subjects should be reminded that if and when appropriate, the Sponsor would offer INO-4800 to those who received placebo in the trial if INO-4800 is demonstrated to be efficacious.

For subjects in the Phase 2 segment of the trial, the receipt of any non-study prophylactic COVID-19 vaccine (authorized under emergency use or licensed) is not restricted, based upon increasing availability of EUA vaccine in the US and completion of the Phase 3 dose selection from the Phase 2 data.

If a subject informs the site of their intent to receive a non-study prophylactic COVID-19 vaccine available either authorized under emergency use or when licensed, the subject should be informed that the safety and effectiveness of receiving INO-4800 followed by another COVID-19 vaccine has not been studied.

Subjects should not participate in any other interventional trials for the duration of this trial.

Subjects must not receive disease modifying doses of anti-rheumatic drugs (e.g., azathioprine, cyclophosphamide, cyclosporine, methotrexate), biologic disease modifying drugs such as TNF- α inhibitors (e.g., infliximab, adalimumab or etanercept) and long term use (\geq 7 days) of oral or parenteral glucocorticoids at a dose of \geq 20 mg/day of prednisone equivalent (use of inhaled, topical, nasal, otic, and ophthalmic corticosteroids are allowed).

